**Table 1: Exclusion criteria**

Allergy or hypersensitivity to PTX or intolerance to methylxanthines (e.g. caffeine, theophylline)
Concurrent use of nephrotoxic drugs
Age less than 18
Pregnancy
Acute or chronic renal replacement therapy at time of enrollment
Shock
TNF alpha antagonist use
Subject is institutionalized or a prisoner
Recent cerebral or retinal hemorrhage (contraindication to PTX)
Previous participation in this study
Severe or poorly controlled cardiovascular disease as determined by the principal investigator to hinder the ability to adhere to study protocols
Creatinine > 4.0 g/dL
Life expectancy $\leq$ 72 hours

## 4. Overall Risk Benefit Assessment

This study is designed to assess the efficacy of PTX use in patients with cirrhosis with ARF when added to standard of hospitalized care. Because of the short duration of dosing and intensive safety assessments, the risks of this study should be minimal to the subjects. Prior studies in both hospitalized and outpatient populations with liver disease have shown PTX to be safe in this population. The risk benefit ratio is minimized in the study design and safety plan.

## 5. Study Objectives

This study is a randomized placebo controlled trial and is hypothesis based. Data on efficacy will be assessed.

5.1. Primary Objective: PTX is safe and effective in treating ARF in hospitalized patients with cirrhosis when added to standard of care

5.2 Secondary and Exploratory Objectives: Progression of ARF to a different stage as defined by AKIN criteria will be assessed.[3] If a patient is enrolled at stage III ARF, they will be considered to have progressed should they be started on renal replacement therapy (RRT). Other secondary endpoints that will be assessed include change in serum creatinine from baseline to day 14, combined increase of treatment success and “partial response” which we define as serum creatinine level decreased by >50% from baseline but not to baseline without dialysis or HRS recurrence, transplant free survival at day 30 and 180, overall survival at day 30 and 180, composite survival index at day 30 and 180.

## 6. Ethical Considerations

### 6.1. Good Clinical Practice

This study will be conducted in accordance with Good Clinical Practice (GCP), as defined by the International Conference on Harmonization (ICH) and in accordance with the ethical principles underlying European Union Directive 2001/20/EC and the United States Code of Federal Regulations, Title 21, Part 50 (21CFR50). The study will be conducted in compliance with the protocol. The protocol and any amendments and the subject informed consent will receive Institutional Review Board/Independent Ethics Committee (IRB/IEC) approval/favorable opinion prior to initiation of the study. All potential serious breaches must be reported to the local IRB as required immediately. A serious breach is a breach of the conditions and principles of GCP in connection with the study or the protocol, which is likely to affect, to a significant degree, the safety or physical or mental integrity of the patients of the study or the scientific value of the study. Study personnel involved in conducting this study will be qualified by education, training, and experience to perform their respective task(s).

### 6.2. Institutional Review Board/Independent Ethics Committee

Before study initiation, the investigator must have written and dated approval/favorable opinion from the IRB/IEC for the protocol, consent form, subject recruitment materials/process (e.g., advertisements), and any other written information to be provided to patients. The investigator or sponsor should provide the IRB/IEC with reports, updates and other information (e.g., expedited safety reports, amendments, and administrative letters) according to regulatory requirements or institution procedures.

### 6.3. Informed Consent

Investigators must ensure that patients are clearly and fully informed about the purpose, potential risks, and other critical issues regarding clinical studies in which they volunteer to participate. Surrogate consent will be sought if the patient is unable to provide consent due to encephalopathy or lack of capacity. Freely given written informed consent must be obtained from every subject prior to clinical study participation, including informed consent for any screening procedures conducted to establish subject eligibility for the study. The rights, safety, and well being of the study patients are the most important considerations and should prevail over interests of science and society. The consent process will occur in a private room in the hospital. The PI will carefully discuss the risks and benefits of study participation and review study procedures. The PI will make it clear that the subject's standard clinical care will not be affected in any way through participation or non-participation in the study. All questions will be answered prior to signing the informed consent document and the subject will verbalize understanding at the time of consent. The consent process will take approximately 15 minutes.

## 7. Study Treatments

### 7.1. Investigational Drug

PTX is a vasoactive xanthine derivative and phosphodiesterase inhibitor that improves peripheral blood flow and enhances peripheral tissue oxygenation. PTX relaxes smooth muscle in peripheral vessels leading to vasodilation. PTX improves red blood cell flexibility, which allows for improved blood flow ability. Importantly, PTX promotes platelet deaggregation and decreases blood viscosity. The summative effects are a decrease in inflammatory mediators. The investigational pharmacy will be used for drug acquisition, storage, and accountability. Subjects will start the protocol with 400mg PTX three times a day for 14 days or the renally dosed equivalent (400mg BID for eGFR 10-50 and 400mg daily for eGFR <10). The investigators will not seek FDA labeling or approved indications for PTX as part of this study; therefore, no IND will be sought for the study drug use in this protocol. There are no restrictions on concurrent drugs other than those listed in the exclusion criteria in Table 1. The study drug cannot be crushed or administered through a nasogastric tube. If a patient is NPO but can swallow safely, they may receive the drug. If they are NPO and have a nasogastric tube in place they will miss the dose.

### 7.2. Study Drug Discontinuation

Study drug or placebo will be discontinued if a grade 3 adverse event (based on the NCI Common Terminology Criteria for Adverse Events, CTCAE, version 4.0) related to the study drug at the judgment of the PI and medical monitor. The PI will notify the medical monitor of a grade 3 adverse event over the phone and the medical monitor will conduct an independent review with access to the medical record. The medical monitor may interview the patient at the bedside should they deem this necessary. Meetings between the medical monitor and the PI will take place on an as needed basis. One scheduled meeting will take place after 50% enrollment has been completed to review all the reported adverse events.

Study drug or placebo will be discontinued if a grade 4 adverse event or pregnancy occurs during the study protocol or at the request of the subject. If the subject misses a dose and is less than 4 hours late, the subject will be advised to make up the dose. Otherwise, the dose can be omitted and per protocol dosing can resume with the next scheduled administration.

### 7.3. Management of Study Drug Side Effects

Because of the short duration of study drug administration, side effects are expected to be minimal. Side effects will be assessed and managed directly by the study team. If severe, the study team will discontinue the study drug. Common side effects of PTX include dyspepsia and nausea. More serious, rare side effects include a hypersensitivity reaction and/or arrhythmia.

## 8. Study Assessments

### 8.1. Schedule of Visits

The schedule of study assessments and visits is shown in Table 2.

Table 2: Schedule of visits and study protocol assessments

Visit	Screening initial assessment	Follow up assessment	"Partial response" assessment	Phone Call
Day	0	Day 3,7,10,14	Day 14, 28	Day 30,180
Initial history and physical exam	X			
ARF response assessment		X	X	X
Symptom triggered physical exam		X	X	
Interim safety assessment and pill count		X	X	
Labs and imaging	X	X	X	

### 8.2. Primary Endpoints

ARF treatment response will be assessed according to Table 2. The PI or sub-investigators will perform all assessments and will assess for the presence of side effects or toxicities of the study drug by performing a brief history at each visit and by performing a targeted physical exam. A phone call to assess 30 and 180-day survival will be completed.

### 8.3. Secondary Endpoints

The secondary endpoints will be assessed by the PI, or sub-investigators, during telephone assessments and in-person hospital visits as noted in Table 2.

## 9. Statistical Procedures and Methods

As this is a pilot study and the benefit of PTX in the treatment of ARF has not been studied, we estimate a sample size of 30, 15 in each treatment arm, is sufficient to meet our primary and secondary endpoints. Results will be expressed as means with standard deviations. Chi-squared and Fisher's exact test will be used to analyze our categorical endpoints. Student's t test and Mann-Whitney Rank Sum test will be used for secondary analysis of differences in numerical lab data. Kaplan-Meier curves will be constructed and compared by a log-rank test to assess our secondary endpoint of all-cause mortality. A p value of  $<0.05$  will be significant. Intention to treat analysis will be performed. Subgroup analysis will be performed by stratifying on initial AKIN stage.

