## **Brief Study Synopsis**

**Study Phase:** Pilot

**Primary hypothesis:** Pentoxyfylline (PTX) therapy at 1200 mg per day or the renally dose equivalent in addition to standard of care is superior to placebo in the treatment of acute renal failure (ARF) not responsive to volume resuscitation in hospitalized patients with cirrhosis.

**Study design:** Prospective, placebo-controlled, randomized pilot trial.

Each hospitalized subject will undergo pre-dosing screening with review of his or her history and physical exam from the day of enrollment and safety assessment to ensure no contraindication to use of PTX.

ARF will be defined according to the definition put forth by and validated prospectively by collaboration between the International Ascites Club (IAC) and the Acute Dialysis Quality Initiative as a rise in creatinine of 0.3 mg/dl or 50% from baseline creatinine, which will be defined as the most recent stable measurement before admission.[1]

Baseline testing will be obtained from hospitalization records, including but not limited to chemistry panel, liver function testing, urinalysis, urine electrolytes, coagulation studies, blood cultures, chest x-ray, diagnostic paracentesis, abdominal ultrasound with Doppler.

Subjects will take either placebo three times a day or PTX 400mg three times a day or 400mg twice a day for eGFR 10-50 and 400mg once a day for eGFR <10 for 14 days in addition to standard inpatient care. Treatment will be continued for 14 days unless a study endpoint has been reached at which time either PTX or placebo will be stopped.

**Total study subjects expected:** 30 patients with cirrhosis hospitalized ARF

**Duration of study:** 180 days

**Study Drugs:** PTX 400 mg tablets and placebo. The study team will not be pursuing a change in labeling or an FDA approved indication for this drug as a part of this proposal. Standard placebo provided in similar tablet forms. All investigational drugs will be prepared by the Investigational Pharmacy by inserting the active drug/placebo into larger cloaking capsules. Standard corn starch will be used inside the placebo capsule.

Randomization will be 1:1. The Investigational Pharmacy will be performing randomization and will generate the block randomization scheme.

**Endpoints:** The primary endpoint is resolution of ARF, defined as a return to baseline creatinine for 24 hours.

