## 2. Study Design

[figure not shown]
The proposed study is a blinded prospective, placebo controlled, randomized pilot study. Figure 1 shows the study design schematic. Subjects will be identified during their hospitalization with ARF. Each subject will undergo screening and a pre-dosing history and physical exam, and safety assessment, which will include reviewing basic blood work results and imaging from their hospitalization (CBC, CMP, INR, Blood cultures, UA and urine culture, Urine lytes, Chest x-ray, Abdominal ultrasound with dopplers, diagnostic paracentesis if ascites is present) and performing urine pregnancy testing in women of child bearing potential. Subjects will be randomized 1:1 by the Investigational Pharmacy.

Subjects will then take a 14-day course of PTX 400 mg three times a day. On day 3 there will be an in-person assessment and review of side effect profile. If there have been no serious adverse events, PTX will be continued. Additional safety assessments will be completed at day 7,10,14.

Patients will also be seen in the hospital to assess for treatment response at day 3,7,10,14. At these visits, they will have repeat blood work at the discretion of the treating physicians (e.g. CBC, CMP, INR, UA with reflex urine culture, Urine lytes,). During each assessment, primary and secondary endpoints will be measured. If an endpoint is obtained, the patient will be instructed to stop therapy.

Survival will be assessed at 30 and 180 days by telephone interviews. If subjects are discharged prior to completing 14 days of therapy, they most likely has met an endpoint (resolution, death, transplant, etc). If in the unlikely event the patient is to be discharged and they have not met an endpoint, they will be withdrawn from the study. Once the patient is discharged there will be no in person follow up evaluations.

Figure 1: Study protocol

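### Survival is compared only by an unadjusted log-rank test in 15 v 15 patients; a Cox model with one pre-specified severity score, reported with a hazard ratio and interval, would use data already collected

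*Combined protocol and SAP*

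**What the plan says.** Section 9 gives the survival method in one sentence: "Kaplan-Meier curves will be constructed and compared by a log-rank test to assess our secondary endpoint of all-cause mortality". The Brief Study Synopsis says the same of its survival endpoints, which include overall and transplant-free survival at days 30 and 180. Follow-up is described in section 2: "Survival will be assessed at 30 and 180 days by telephone interviews". Neither place names a Cox model, a stratified test, a covariate, a hazard ratio or a confidence interval.

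The sample size is asserted: "we estimate a sample size of 30, 15 in each treatment arm, is sufficient to meet our primary and secondary endpoints". The significance rule is "A p value of $<0.05$ will be significant", with sidedness not stated.

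Allocation is 1:1. The synopsis says that "The Investigational Pharmacy will be performing randomization and will generate the block randomization scheme", and no stratification factor is given. The one analysis that uses baseline severity is in section 9: "Subgroup analysis will be performed by stratifying on initial AKIN stage".

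The laboratory data for a severity score are reviewed at entry. The synopsis lists "chemistry panel, liver function testing, urinalysis, urine electrolytes, coagulation studies" and section 2 lists "CBC, CMP, INR, Blood cultures, UA and urine culture". Bilirubin is not named; I infer it from the liver function tests and the CMP.

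**The concern.** The documents describe patients of very mixed prognosis. Section 1 divides ARF in cirrhosis into pre-renal azotemia, ATN and hepatorenal syndrome, and puts life expectancy in type 1 HRS at under two weeks. Blocked randomisation balances the number per arm, not severity. In 30 patients the arms may well differ in severity at entry, and nothing in the planned comparison takes that into account. The AKIN analysis splits 30 patients into small groups and yields no adjusted overall comparison.

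Two things are at stake. One is efficiency: a covariate that predicts death, already measured, goes unused where information is scarcest. The other is usefulness. The synopsis says that a benefit here would lead to an application for a larger trial. The Kaplan-Meier curves will estimate survival in each arm, but no between-arm effect with an interval is planned, and a log-rank p value from 30 patients tells the designer of that trial little.

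**Working it through.** **Inputs from the documents.** 15 per arm, alpha 0.05 (taken as two-sided), follow-up to day 180. No event rate, effect size or power is stated, so the figure of 30 cannot be reproduced. The only mortality rates by arm are those of the alcoholic hepatitis trial cited in section 1: 24.5% on PTX and 46.1% on placebo. I use them as a benchmark, not as a planning input.

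**Power of the planned test at those rates.**
- Hazard ratio under proportional hazards: ln(1 − 0.245)/ln(1 − 0.461) = 0.455.
- Expected deaths: 15 × (0.245 + 0.461) = 10.6.
- Schoenfeld: ½√10.6 × |ln 0.455| − 1.96 = −0.68, so power is about 25%.
- Deaths needed for 80% power: 4 × (1.96 + 0.84)²/(ln 0.455)² ≈ 51. If all 30 patients died, power would be about 58%.

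**Chance imbalance.** The difference between arm means of a score has SD √(2/15) = 0.365 in SD units. P(|difference| > 0.5 SD) = P(|Z| > 1.37) = 17%. At an assumed log hazard of 0.8 per SD, a difference of 0.5 SD alone corresponds to a hazard ratio of exp(±0.4), about 1.5 or 0.67.

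**Effect of adjustment, marginal mortality held fixed.** 10,000 simulated trials per setting, exponential survival, normal score. Prognostic strength is an assumption, as is the higher mortality pair. Power in %:

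| Log hazard per SD | 0 | 0.5 | 0.8 | 1.2 |
|---|---|---|---|---|
| *46.1% v 24.5%, 10.6 deaths* | | | | |
| Log-rank | 23.2 | 23.9 | 25.3 | 24.7 |
| Cox + score, likelihood ratio | 24.8 | 27.2 | 31.4 | 37.4 |
| Cox + score, Wald | 17.1 | 19.6 | 23.7 | 30.2 |
| *70% v 40%, 16.5 deaths* | | | | |
| Log-rank | 40.6 | 41.2 | 42.8 | 44.1 |
| Cox + score, likelihood ratio | 40.6 | 45.7 | 55.3 | 69.4 |
| Cox + score, Wald | 37.6 | 43.1 | 52.6 | 67.0 |

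With no treatment effect, rejection rates were 5.0 to 5.5% (log-rank), 5.4 to 6.1% (likelihood ratio) and 4.5 to 5.4% (Wald).

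**Effect of adjustment, hazard ratio given the score fixed at 0.4.** With 13 to 17 deaths, and log hazard 0.5, 0.8 and 1.0 per SD, unadjusted power was 32, 31 and 26% and likelihood-ratio power 36, 38 and 36%: gains of 4, 7 and 10 points. Further runs with about 12 to 16 deaths gave gains of about 4 to 5, 8 to 9 and 10 to 15 points. At 0.5 the Wald test gained essentially nothing (31 to 39% against 32 to 39% for the log-rank). With a score of no prognostic value it lost about 3 to 5 points.

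**Reading.** The gain depends on the strength of the score and on the test. At the cited trial's rates the Wald test lies below the log-rank at 0.5 and 0.8. No setting reaches 80% power.

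**The case against.** The strongest reply is that nothing here is wrong. A log-rank test is valid under randomisation. Chance imbalance is already inside its 5% error rate, as the null simulations confirm. A reader might take the 17% as an excess risk of a false-positive result; it is not. It is the chance that one score differs noticeably between arms, and it matters for interpreting the one trial observed, not for the long-run validity of the test. This stands.

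Three other inferences also go too far:
- *Adjustment will raise power.* The documents give no prognostic strength for any laboratory value. The exclusions in Table 1 (a creatinine ceiling, shock, very short life expectancy) narrow the spread of severity. With a weak score the gain is nil or small, and part of the likelihood-ratio gain reflects type I error slightly above 5%.
- *Adjustment removes chance imbalance.* It corrects for imbalance in that one score, under the model. Imbalance in the cause of ARF, for example, remains.
- *The unadjusted hazard ratio is biased towards 1.* It is a marginal quantity, and the adjusted one is conditional on the score. They differ because hazard ratios are non-collapsible, not because the planned test is biased.

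The objection does not remove the case for the change: the laboratory data are in hand, no effect estimate with an interval is planned, and a covariate chosen after the data are seen would be open to selection.

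**Conclusion.** The point holds as an optional, low-cost improvement to a secondary analysis. The survival comparison is unadjusted, has no planned between-arm estimate, and leaves collected severity data unused. The gain is about 4 to 15 points of power by likelihood-ratio test, with type I error of about 5 to 7%. It rests on assumed log hazards of 0.5 to 1.0 per SD, a hazard ratio of 0.4 and about 12 to 17 deaths, none of which is in the documents. At the mortality of the cited alcoholic hepatitis trial, with about 10.6 deaths, the gain is 27.2 − 23.9 = 3.3 points at 0.5 and 31.4 − 25.3 = 6.1 points at 0.8.

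The documents do not support calling the log-rank test an error, and adjustment does not rescue the survival endpoint, which is underpowered with or without it.

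**What to change.** In section 9, and in the matching paragraph of the synopsis:
- Make the adjusted survival analysis a Cox model with treatment arm and one severity score, for overall and for transplant-free survival.
- Define the score by formula, from the last bilirubin, INR and creatinine before randomisation. State that this is the enrolment creatinine. The synopsis and section 3 define baseline creatinine as the last stable value before admission, so the word baseline alone would point to the wrong measurement. Confirm that bilirubin is recorded.
- Test arm by likelihood ratio, and report the hazard ratio with a profile-likelihood 95% CI, described as conditional on the score.
- Keep the Kaplan-Meier curves and the log-rank test as the unadjusted analysis.
- State that survival is underpowered and that the estimate and its interval are the result of interest.

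The cost is a few lines of text and no new data. With so few deaths the model can carry only one covariate, so it must be fixed before unblinding. If the score turns out to be weakly prognostic, little or nothing is gained.

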## 10. Adverse Events, Human Safety Measures, and Oversight

### 10.1. Definitions

An Adverse Event (AE) is defined as any new untoward medical occurrence or worsening of a pre-existing medical condition in a patient or clinical investigation subject administered an investigational (medicinal) product and that does not necessarily have a causal relationship with this treatment. An AE can therefore be any unfavorable and unintended sign, symptom, or disease temporally associated with the use of investigational product, whether or not considered related to the investigational product.

### 10.2. Serious Adverse Events

A serious AE (SAE) is any untoward medical occurrence that at any dose:

- results in death
- is life-threatening (defined as an event in which the subject was at risk of death at the time of the event; it does not refer to an event which hypothetically might have caused death if it were more severe)
- requires inpatient hospitalization or causes prolongation of existing hospitalization (see note below for exceptions)
- results in persistent or significant disability/incapacity
- results in a congenital anomaly/birth defect
- is an important medical event (defined as a medical event(s) that may not be immediately life-threatening or result in death or hospitalization but, based upon appropriate medical and scientific judgment, may jeopardize the subject or may require intervention [e.g., medical, surgical] to prevent one of the other serious outcomes listed in the definition above.) Examples of such events include, but are not limited to, intensive treatment in an emergency room or at home for severe encephalopathy; seizures or convulsions that do not result in hospitalization.)

All pregnancies, regardless of outcome, will be considered a special adverse event (not an SAE). Although overdose and cancer are not always serious by regulatory definition, these events should be reported as an SAE in an expedited manner.

